5.2.2 Endpoint Selection

5.2.2.1 Part 1, M8891 Single Agent, Solid Tumors

The study endpoints are standard Phase I endpoints, namely to define the safety and PK of the drug in humans, and activity in terms of tumor growth control (using RECIST v1.1 guidelines) for solid tumors in subjects with advanced disease with no other therapeutic options, and toxicity.

CCI

5.2.2.2 Part 2, M8891 Combined with Cabozantinib, mRCC

The study endpoints are standard Phase Ib endpoints, namely to define that the combination of M8891 and cabozantinib is safe and tolerable in subjects with mRCC who have progressed to one or more previous lines of therapies (See Section 5.1). The efficacy of the combination therapy will be determined by the ORR with response including complete and partial response rate/proportion as assessed by RECIST v1.1 criteria.

5.2.3 Inclusion of Special Populations

Not applicable.

5.3 Selection of Trial Population

Only persons meeting all inclusion criteria and no exclusion criteria may be enrolled into the trial as subjects. Prior to performing any trial assessments not part of the subject's routine medical care, the Investigator will ensure that the subject or the subject's legal representative has provided written informed consent following the procedure described in Section 9.2.

5.3.1 Inclusion Criteria

5.3.1.1 Part 1, M8891 Single Agent, Solid Tumors

Subjects are eligible to be included in the study only if all the following criteria apply:

1. Subjects must be refractory to or intolerant of existing cancer therapy(ies) known to provide clinical benefit.
2. Histologically confirmed advanced solid tumors with no clear curative treatment options available after at least 1 prior systemic anticancer therapy
3. Male and female subjects age 18 years and older who are able and willing to give written informed consent
4. A male subject must agree to use and to have their female partners to use a highly effective contraception (i.e., methods with a failure rate of less than 1% per year) as detailed in [Appendix I](#) of this protocol before first dose of study treatment (as appropriate), during the treatment period and for at least 92 days (3 months) after the last dose of study treatment and refrain from donating sperm during this period.
5. A female subject is eligible to participate if she is not pregnant (see [Appendix I](#)), not breastfeeding, and at least one of the following conditions applies:
 - a. Not a woman of childbearing potential (WOCBP) as defined in [Appendix I](#)
 - b. A WOCBP who agrees to use a highly effective contraception (i.e., methods with a failure rate of less than 1% per year) as detailed in [Appendix I](#) of this protocol before start of first dose of study treatment (as appropriate), during the treatment period and for at least 92 days (3 months) after the last dose of study treatment.
6. Tumor accessible for biopsies and agreement to conduct pre-dose and post-dose fresh tumor biopsies. Archival tumor tissue is not mandatory for the inclusion in the study but is strongly recommended.

5.3.1.2 Part 2, M8891 combined with Cabozantinib, mRCC

Subjects are eligible to be included in the Part 2 of the study only if all the following criteria apply:

1. Male and female subjects age 18 years and older who are able and willing to give written informed consent before the performance of any study-specific procedures.
2. Eastern Cooperative Oncology Group Performance Status (ECOG PS) of 0 to 1 at Screening.
3. Histologic or cytologic evidence/proven of mRCC with clear cell component.
4. Previous treatments:
 - a. **Part 2A:** Subjects should have progressed to 1 or more previous lines of systemic anticancer therapy, excluding treatment with cabozantinib.
 - b. **Part 2B:** Subjects should have progressed to 1 or 2 previous lines of systemic anticancer therapy, excluding treatment with cabozantinib. Subjects should have failed to only 1 previous TKI for metastatic disease. Adjuvant therapy with sunitinib will be considered as 1 line of therapy for metastatic disease in the case that disease progression occurs during or within 3 months of the completion of the treatment.
5. At least 1 lesion that is measurable using RECIST v1.1.
6. Ability to swallow capsules and tablets.
7. Recovery from any acute toxicities from the previous therapy to Grade 1.
8. Predicted life expectancy of > 3 months (according to the opinion of the Investigator).
9. Adequate organ function (i.e. liver, kidney, bone marrow), as evidenced by multiple laboratory value results within specific parameters. Specifically:
 - Hemoglobin \geq 9.0 g/dL (no transfusion in the past 2 weeks before first dose); neutrophil count $>$ 1.5 \times 10⁹/L; platelets $>$ 100 \times 10⁹/L (no transfusion in the past 2 weeks before first dose).
 - Glomerular filtration rate \geq 30 mL/min (according to the Cockcroft-Gault formula)
 - Total bilirubin \leq 1.5 \times ULN, AST/ALT \leq 2.5 \times ULN. For documented Gilbert's syndrome a total bilirubin $<$ 3 \times ULN is accepted.
10. Patients with central nervous system (CNS) metastases must have received surgical and/or radiation treatment and be neurologically stable no evidence of CNS disease progression as determined by CT or MRI within 21 days prior to the first dose of study drug.
11. Subjects on bisphosphonates may continue receiving bisphosphonates therapy during study treatment.
12. A male subject must agree to use and to have their female partners use a highly effective contraception (i.e., methods with a failure rate of less than 1% per year) as detailed in [Appendix I](#) of this protocol before first dose of study treatment (as appropriate), during the treatment

period and for at least 92 days (3 months) after the last dose of study treatment and refrain from donating sperm during this period.

13. A female subject is eligible to participate if she is not pregnant (see [Appendix I](#)), not breastfeeding, and at least one of the following conditions applies:

a. Not a woman of childbearing potential (WOCBP) as defined in [Appendix I](#)

OR

b. A WOCBP:

- who agrees to use a highly effective contraception (i.e., methods with a failure rate of less than 1% per year) as detailed in Appendix I of this protocol before start of first dose of study treatment (as appropriate), during the treatment period and for at least 92 days (3 months) after the last dose of study treatment.
- Who has a negative serum pregnancy test at the Screening Visit and a negative urine pregnancy test on Day 1 before dosing, as required by local regulations, within 24 hours before the first dose of study intervention.

5.3.2 Exclusion Criteria

5.3.2.1 Part 1, M8891 Single Agent, Solid Tumors

For Part 1, subjects are excluded from the study if any of the following criteria apply:

1. Eastern Cooperative Oncology Group Performance Status (ECOG PS) ≥ 2
2. Bone marrow impairment as evidenced by hemoglobin < 9.0 g/dL, neutrophil count $< 1.5 \times 10^9/L$, platelets $< 100 \times 10^9/L$. Transfusion is not allowed within 3 weeks before first dose
3. Renal impairment as evidenced by calculated creatinine clearance < 60 mL/min (according to the Cockcroft-Gault formula)
4. Liver function abnormality as defined by total bilirubin $> 1.5 \times$ ULN, or AST/ALT $> 2.5 \times$ ULN, for subjects with liver involvement AST/ALT $> 5 \times$ ULN
5. Extensive prior radiotherapy to more than 30% of bone marrow reserves, or prior bone marrow/stem cell transplantation within 5 years of study start
6. Clinically significant cardiac conduction abnormalities, including QTcF interval prolongation of > 480 ms and/or pacemaker or impaired cardiovascular function such as New York Heart Association classification score > 2
7. Thromboembolic events requiring therapeutic anticoagulation. Concomitant anticoagulation at therapeutic doses with oral anticoagulants (i.e., warfarin, direct thrombin

and Factor Xa inhibitors) or platelet inhibitors (i.e., clopidogrel) started within the last 6 months of screening.

Note: Low dose aspirin for cardio-protection and low dose LMWH are permitted (in subjects who are on a stable dose of LMWH for at least 6 weeks before the first dose of study treatment, and who have had no clinically significant hemorrhagic complications from the anticoagulation regimen or the tumor).

[figure not shown]
8. Pregnant or nursing female subject
9. Any other severe clinical condition that in the opinion of the treating physician may compromise the trial participation
10. Subjects used any investigational agents 14-28 days or 5-half-lives (whichever is shorter) of the initiating study treatment
11. History of difficulty swallowing, malabsorption, or other chronic gastrointestinal disease or conditions that may hamper compliance and/or absorption of the investigational drugs
12. Life expectancy < 3 months
13. Known hypersensitivity to the trial treatment or to one or more of the excipients used
14. Legal incapacity or limited legal capacity.

5.3.2.2

Part 2, M8891 combined with Cabozantinib, mRCC

For both Part 2A and Part 2B, subjects are excluded from the study if any of the following criteria apply:

1. Previous use of cabozantinib or a MetAP2 inhibitor.
2. Receipt of other anticancer therapy within 2-4 weeks (wash-out period of 5 half-lives) or radiotherapy within 1 week prior to first dose of study treatment or patients who have not recovered from the side effects of such therapy to Baseline or Grade 1 (except for alopecia or potentially neuropathy).
3. Subjects used any investigational agents 14-28 days or 5-half-lives (whichever is shorter) of the initiating study treatment.
4. Tumor in contact with, invading or encasing major blood vessels or radiographic evidence of significant cavitary pulmonary lesions.
5. Pathologic evidence of tumor invading the gastrointestinal tract, or any evidence of endotracheal or endobronchial tumor within 28 days before the first dose of study treatment.

6. Clinically significant hematuria, hematemesis, or hemoptysis of > 0.5 teaspoon (2.5 mL) of red blood, or other history of significant bleeding (e.g. pulmonary hemorrhage) within 3 months before the first dose of study treatment.
7. Major surgery within 12 weeks before the first dose of study treatment. Complete wound healing from major surgery must have occurred 1 month before the first dose of study treatment. Minor surgery within 28 days before the first dose of study treatment. Complete wound healing from minor surgery must have occurred at least 10 days before the first dose of study treatment.
8. Active symptomatic fungal, bacterial (requiring IV antibiotics) and/or viral infection. Individuals with known or seropositive testing for human immunodeficiency virus (HIV) or actively infected viral hepatitis (B or C) are excluded. However, individual with Hepatitis C treated with curative therapy are not considered actively infected.
9. Uncontrolled hypertension defined as sustained Blood Pressure (BP) > 150 mm Hg systolic or > 100 mm Hg diastolic despite optimal antihypertensive treatment.
10. Current significant cardiac conduction abnormalities, including QTcF interval prolongation of > 450 ms for males and > 470 ms for females or cardiovascular disorders, including symptomatic congestive heart failure, unstable angina pectoris, and serious cardiac arrhythmias.
11. The subject is pregnant or breastfeeding.
12. Cerebrovascular accident/stroke (< 6 months prior enrollment) or neurologic instability per clinical evaluation due to tumor involvement of the CNS.
13. Thromboembolic events requiring therapeutic anticoagulation. Concomitant anticoagulation at therapeutic doses with oral anticoagulants (i.e., warfarin, direct thrombin and Factor Xa inhibitors) or platelet inhibitors (i.e., clopidogrel) started within the last 6 months of screening.

Note: Low dose aspirin for cardio-protection and low dose LMWH are permitted (in subjects who are on a stable dose of LMWH for at least 6 weeks before the first dose of study treatment, and who have had no clinically significant hemorrhagic complications from the anticoagulation regimen or the tumor).
14. Presence of clinically significant cardiac, respiratory, or other medical or psychiatric condition that might interfere with participation in the trial or interfere with the interpretation of trial results.
15. History of allergic reactions attributed to compounds of similar chemical or biologic composition to cabozantinib or M8891.
16. An active second malignancy or evidence of disease of cancer (other than RCC) before the date of enrollment (exceptions are squamous and basal cell carcinomas of the skin and carcinoma in situ of the cervix, or malignancy that in the opinion of the Investigator, with

concurrence with the Sponsor's medical monitor, is considered cured with minimal risk of recurrence within 3 years).

5.4 Criteria for Initiation of Trial Treatment

Not applicable.

5.5 Criteria for Subject Withdrawal

5.5.1 Withdrawal from Trial Therapy

[figure not shown]
A subject must be withdrawn from M8891 if any of the following occur:

- Subject withdrew consent
- Subject lost to follow up
- Participation in another clinical trial
- Any events that unacceptably endanger the safety of the subject
- Discontinuation is considered necessary by the Investigator and/or Sponsor due to occurrence of an exclusion criterion or AE which is clinically relevant and affects the subject's safety
- Discontinuation of M8891 (or M8891 combined with cabozantinib) is desired or considered necessary by the Investigator and/or the subject (if applicable) due to occurrence of > Grade 2 AEs for more than 6 days
- If at any time on study the average QTcF interval from the 3 ECGs is > 500 ms and
 - Cardiac evaluation confirms that symptoms are the consequence of QT interval prolongation or
 - Recurrence of QTcF interval prolongation after reinitiation of study treatment at a reduced dose (see Section 6.5.5 for cabozantinib)
- Any DLTs as described in Section 5.1.
- Stroke (including transient ischemic attack, TIA), myocardial infarction, or other ischemic event, or thromboembolic event (e.g., deep venous thrombosis, pulmonary embolism)
- Occurrence of pregnancy
- Noncompliance that is deemed by the Investigator or the Sponsor to compromise the subject's safety or trial integrity.

5.5.2 Withdrawal from the Trial

A subject may withdraw from the study at any time, at his/her own request without giving a reason or may be withdrawn at any time at the discretion of the Investigator for safety, behavioral, compliance, or administrative reasons.

A subject must be withdrawn if any of the following occur during the trial:

- Subject withdrew consent
- Documented disease progression (see Section 5.3.1.1 for exception)
- Lost to follow-up
- Noncompliance that is deemed by the Investigator or the Sponsor to compromise the subject's safety or trial integrity
- Occurrence of AEs for which discontinuation is desired or considered necessary by the Investigator and/or the subject
- Participation in any other interventional trial during the duration of treatment in this trial.

At the time of discontinuing from the study, an EOT visit will be conducted, as listed in the SoAs. The SoAs specifies the data to collect at EOT and follow-up, and any additional evaluations that need to be completed.

If the subject withdraws consent for future involvement in the study, any data collected up to that point may still be used, but no future data can be generated, and any biological samples collected after consent withdrawal will be destroyed.

A subject has the right at any time to request destruction of any biological samples taken. The Investigator must document this in the site study records.

If a subject has failed to attend scheduled trial assessments, the Investigator must determine the reasons and the circumstances as completely and accurately as possible.

During dose escalation (Part 1 and Part 2A), subjects who prematurely discontinue treatment during Cycle 1 for any other than DLT reason, will be replaced to reach a minimum of 2 evaluable subjects in each cohort. Subjects discontinuing due to DLT in Cycle 1 are not replaced.

5.6 Premature Termination of the Trial

The clinical trial may be terminated prematurely or suspended at the request of Health Authorities or if new safety or efficacy information leads to an unfavorable risk benefit judgment for any Investigational Medicinal Product (IMP). The Sponsor may discontinue the trial if it becomes unjustifiable for medical or ethical reasons, for poor enrollment, or because of discontinuation of clinical development of an IMP or withdrawal of an IMP or comparator from the market for safety reasons.

The whole trial may be discontinued prematurely in the event of any of the following:

- New information leading to unfavorable risk-benefit judgment of M8891 (or M8891 combined with cabozantinib), e.g., due to:
 - Evidence of inefficacy of M8891 (or M8891 combined with cabozantinib)
 - Occurrence of significant previously unknown adverse reactions or unexpectedly high intensity or incidence of known adverse reactions
 - Other unfavorable safety findings.

(Note: evidence of inefficacy may arise from this trial or from other trials; unfavorable safety findings may arise from examinations within clinical or nonclinical studies, e.g., toxicology.)

- Sponsor's decision that continuation of the trial is unjustifiable for medical or ethical reasons
- Poor enrollment of subjects making completion of the trial within an acceptable time frame unlikely
- Discontinuation of development of M8891.

Health Authorities and Independent Ethics Committees (IECs)/Institutional Review Boards (IRBs) will be informed about the discontinuation of the trial in accordance with applicable regulations.

5.7 Definition of End of Trial

A clinical trial protocol may not be considered closed as long as:

- Any subject is still receiving any IMP
- Visits specified by the protocol are still taking place
- Procedures or interventions according to the protocol are still being undertaken in any subject
- The post-treatment follow-up period, defined in the clinical trial protocol as being part of the trial, has not yet been completed for any subject.

If the trial is not prematurely discontinued for a reason given in Section 5.6, the end of the trial is defined as the last subject enrolled in the trial having treatment up to 2 years or either stopped M8891 (or M8891 combined with cabozantinib), i.e., having withdrawn because of disease progression, death, unacceptable toxicity, or Investigator/subject decision, or having completed the EOT visit and Safety Follow-up visit if applicable. Subjects who are on ongoing treatment at this time may be offered continued treatment outside of the study under observation of local regulations.

[figure not shown]
6 Investigational Medicinal Product and Other Drugs Used in the Trial

The term “Investigational Medicinal Product” (IMP) refers to an active substance or a placebo being tested or used as a reference therapy in a clinical trial, including products that have a marketing authorization but are formulated, packaged, or administered differently from the authorized form, used for an unauthorized indication, or used to gain further information about the authorized form. The IMP for this study is M8891.

6.1 Description of the Investigational Medicinal Product

6.1.1 M8891

The chemical name of M8891 drug substance is (S)-3-Hydroxy-1-(1H-indol-5-yl)-2-oxo-pyrrolidine-3-carboxylic acid 3,5-difluoro-benzylamide.

M8891 is formulated as 1 mg (size “3”, color white), 5 mg (size “3”, color white) and 30 mg (size 0, color Swedish orange) hard gelatin capsules for oral administration. No other excipients are used.

6.1.2 Cabozantinib (Cabometyx)

Cabozantinib is indicated for the treatment of patients with mRCC, metastatic medullary thyroid cancer and hepatocellular carcinoma. The approved dosage of cabozantinib in mRCC is 60 mg once daily without food until the patient no longer experiences clinical benefit or experiences unacceptable toxicity. Cabozantinib malate is the (S)-malate salt of cabozantinib, a kinase inhibitor. Cabozantinib (S)-malate is described chemically as N-(4-(6,7-dimethoxyquinolin-4-yl)phenyl)-N’-(4-fluorophenyl)cyclopropane-1,1-dicarboxamide,(2S)-hydroxybutanedioate. The commercial cabozantinib drug product tablet formulation (Cabometyx; Exelixis, Inc.) is marketed in three strengths (20, 40, and 60 mg). Complete information for cabozantinib may be found in the USPI ([Cabometyx USPI 2019](#)).

6.2 Dosage and Administration

6.2.1 Part 1, M8891 Single Agent, Solid Tumors

M8891 will be administered orally as single agent continuously in 21-day cycles at the starting dose of 7 mg QD. In subsequent cohorts subjects will take the total assigned dose of M8891 once daily in the morning with a full glass of water (approximately 240 mL/8 fluid ounces). The subjects should be instructed to swallow the capsules whole and not to bite into the capsules, break or open them, or attempt to dissolve the contents in water prior to taking their assigned dose.

M8891 will be taken under fasted conditions in the morning before breakfast (i.e. at least 2 hours fasted) and subjects will be instructed to continue to fast for 1 hour post-dosing.

Except for water consumed with M8891 administration, water will be withheld for 1 hour before and 1 hour after dose administration.

Dose escalation is described in Section 5.1.3.1

6.2.2 Part 2, M8891 with Cabozantinib, mRCC

In Part 2A M8891 will be administered orally at a starting dose of 20 mg QD combined with cabozantinib continuously in 21-day cycles.

Dose escalation is described in Section 5.1.3.2.1.

CCI

Cabozantinib will be used at the approved 60 mg FBE daily dosage with dosage adjustments to 40 or 20 mg permitted to manage AEs (Section 5.1.3.5).

When the MTD/RDE has been defined in Part 2A (Section 5.1.3.4), the Part 2B expansion cohort with M8891 combined with cabozantinib will be initiated.

In Part 2 **CCI**, M8891 combined with cabozantinib will be taken under fasted conditions in the morning before breakfast (i.e. at least 2 hours fasted) and subjects will be instructed to continue to fast for 1 hour post-dosing. Except for water consumed with M8891 and cabozantinib administration, water will be withheld for 1 hour before and 1 hour after dose administration.

6.3 Assignment to Treatment Groups

Not applicable. This is a single-arm open-label study.

6.4 Non-investigational Medicinal Products to be Used

Not applicable.

6.5 Concomitant Medications and Therapies

All concomitant medications taken by the subject during the trial, from the date of signature of informed consent are to be recorded in the appropriate section of the electronic case report form (eCRF), noting the name, dose, duration and indication of each drug. Nondrug interventions and any changes to a concomitant medication or other intervention should also be recorded in the eCRF.

6.5.1 Permitted Medicines

Any medications that are considered necessary to protect subject welfare and will not interfere with the trial medication may be given at the Investigator's discretion, e.g. hormone therapy is allowed for subjects with prostate cancer.

Rescue medications may be administered to address ineffective treatment, anticipated adverse reactions or anticipated emergency situations.

6.5.2 Prohibited Medicines

6.5.2.1 Part 1, M8891 Single Agent, Solid Tumors

Not applicable for Part 1.

6.5.2.2 Part 2, M8891 with Cabozantinib, mRCC

For cabozantinib the investigators should refer to Section 7 of the cabozantinib USPI ([Cabometyx USPI 2019](#)).

6.5.3 Other Interventions

Not applicable.

6.5.4 Special Precautions

Subjects will be instructed to avoid or to replace medications that are potent combined inhibitors of CYP3A4, CYP2C9 and CYP2C19 (i.e. fluconazole and voriconazole) during treatment of M8891. (See [Appendix II](#) for details).

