Appendix II Drugs which are potent combined CYP2C9, CYP2C19 and CYP3A4 inhibitors

Table 14 contains a list of drugs which are combined potent inhibitors of CYP2C9, CYP2C19 and CYP3A4 (moderate and/or potent inhibitors for at least 2 of the CYP enzymes).

Table 14 Combined Potent Inhibitors

	Strong inhibitors	Moderate inhibitors	Weak inhibitors
CYP2C9	-	amiodarone, felbamate, fluconazole ^(a) , miconazole, piperine	diosmin, disulfiram, fluvastatin, fluvoxamine ^(b) , voriconazole
CYP2C19	Fluconazole ^(a) , fluoxetine ^(c) , fluvoxamine ^(b) , ticlopidine	-	omeprazole, voriconazole
CYP3	boceprevir, cobicistat ^(d) , conivaptan ^(d) , danoprevir, ritonavir ^(e) , elvitegravir, grapefruit juice ^(f) , indinavir, itraconazole ^(d) , ketoconazole, lopinavir, paritaprevir, ombitasvir, dasabuvir ^(e) , posaconazole, saquinavir, telaprevir ^(d) , tipranavir, troleandomycin, voriconazole, clarithromycin ^(d) , diltiazem ^(d) , idelalisib, nefazodone, nelfinavir ^(d)	aprepitant, cimetidine, ciprofloxacin, clotrimazole, crizotinib, cyclosporine, dronedarone ^(d) , erythromycin, fluconazole ^(a) , fluvoxamine ^(a) , imatinib, tofisopam, verapamil ^(d)	chlorzoxazone, cilostazol, fosaprepitant, istradefylline, ivacaftor ^(d) , lomitapide, ranitidine, ranolazine ^(d) , tacrolimus, ticagrelor ^(d)

- a) Strong inhibitor of CYP2C19 and moderate inhibitor of CYP2C9 and CYP3A.
- b) Strong inhibitor of CYP1A2 and CYP2C19, and moderate inhibitor of CYP2D6 and CYP3A. Strong inhibitor of CYP2C8, weak inhibitor of CYP2B6, and inhibitor of OATP1B1.
- c) Strong inhibitors of CYP2C19 and CYP2D6.
- d) Inhibitor of P-gp (defined as those increasing AUC of digoxin to ≥ 1.25 -fold).
- e) Ritonavir is usually given in combination with other anti-HIV or anti-HCV drugs in clinical practice. Caution should be used when extrapolating the observed effect of ritonavir alone to the effect of combination regimens on CYP3A activities.
- f) The effect of grapefruit juice varies widely among brands and is concentration-, dose-, and preparation-dependent. Studies have shown that it can be classified as a "strong CYP3A inhibitor" when a certain preparation was used (e.g., high dose, double strength) or as a "moderate CYP3A inhibitor" when another preparation was used (e.g., low dose, single strength).

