601	Important	IP Admin/Study Treat	Observable	Noncompliance that is deemed by the Investigator or the Sponsor to compromise the patient's safety or trial integrity" but subject was not withdrawn	Source Data Review	
548	Important	Visit Schedule	Programmable	Missing data for safety (hematology, biochemistry, coagulation).	Off-Line Manual Listing	
700	Important	Disallowed Medications	Observable	Subjects taken potent combined inhibitors of CYP3A4, CYP2C9 and CYP2C19 (i.e. fluconazole and voriconazole) during treatment of M8891.	Source Data Review	Yes
549	Important	Visit Schedule	Programmable	End of Treatment Visit not performed.	Off-Line Manual Listing	
604	Important	IP Admin/Study Treat	Programmable	>4 missed administration in Cycle 1 and subject did not have a DLT Subjects is not refractory	Off-Line Manual Listing	Yes
219	Important	Inc/Excl Criteria	Observable	to or intolerant of existing cancer therapy(ies) known to provide clinical benefit	Source Data Review	

PD REF ID	Category (DVCAT)	Classification (DVDECOD)	Type of Deviation Observable/ Programmable (Data Driven)	PD (DVTERM	PD Identification Method Options	cIPD ?
220	Important	Inc/Excl Criteria	Observable	Protocol version 1.0: Presence of deep vein thrombosis based on screening lower extremity Doppler ultrasonography, or elevated D-dimer (> 0.5µg/mL) but subject enrolled in the study.	Source Data Review	
224	Important	Inc/Excl Criteria	Observable	Protocol version 2.0: Presence of deep vein thrombosis based on screening lower extremity Doppler ultrasonography but subject enrolled in the study.	Source Data Review	
221	Important	Inc/Excl Criteria	Observable	Missing data for complete neurologic examination	Source Data Review	
553	Important	Visit Schedule	Observable	A whole visit at the site is not performed	Source Data Review	

Integrated Analysis Plan for end of monotherapy dose escalation - Main Text Body

ELECTRONIC SIGNATURES

Signed by	Meaning of Signature	Server Date (dd-MMM-yyyy HH:mm 'GMT'Z)
PPD	Business Approval	PPD
PPD	Technical Approval	PPD
PPD	Technical Approval	PPD
PPD	Technical Approval	PPD

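### Section 6.5.4 and the rule in Appendix II identify different drugs as the combined CYP inhibitors to avoid with M8891

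*Protocol*

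**What the plan says.** Protocol section 6.5.4 (Special Precautions) instructs subjects to avoid or substitute "potent combined inhibitors of CYP3A4, CYP2C9 and CYP2C19 (i.e. fluconazole and voriconazole) during treatment of M8891" and sends the reader to Appendix II for details.

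Appendix II introduces Table 14 as a list of combined potent inhibitors of the three enzymes and gives the criterion in brackets: "moderate and/or potent inhibitors for at least 2 of the CYP enzymes". Table 14 then grades drugs as strong, moderate or weak, enzyme by enzyme. The cells that matter here are:

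- CYP2C9, moderate: "amiodarone, felbamate, fluconazole ^(a) , miconazole, piperine"
- CYP2C9, weak: "diosmin, disulfiram, fluvastatin, fluvoxamine ^(b) , voriconazole"
- CYP2C19, weak: "omeprazole, voriconazole"
- CYP2C19, strong: includes fluconazole and fluvoxamine
- CYP3, strong: includes voriconazole
- CYP3, moderate: includes fluconazole and fluvoxamine

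Footnote b restates fluvoxamine's grades: "Strong inhibitor of CYP1A2 and CYP2C19, and moderate inhibitor of CYP2D6 and CYP3A". The note under the table calls its entries examples and says that the list is not exhaustive.

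SAP section 18.1, deviation 700, filed under disallowed medications and marked as clinically important, reads "Subjects taken potent combined inhibitors of CYP3A4, CYP2C9 and CYP2C19 (i.e. fluconazole and voriconazole) during treatment of M8891". Protocol section 6.5.2.1, on prohibited medicines, says "Not applicable for Part 1".

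**The concern.** The abbreviation i.e. presents fluconazole and voriconazole as the members of the class, while the appendix cited for details defines the class by a rule that gives a different pair. A site that works from section 6.5.4 alone would leave fluvoxamine in place, although it meets the protocol's own criterion. It would replace voriconazole, which does not meet that criterion.

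The distinction matters to the plan. Section 3.3.1 predicts only a weak effect on M8891 from strong inhibitors of these enzymes, but a moderate one from a combined inhibitor. Deciding which drugs count as combined is therefore the purpose of the precaution.

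On the analysis side, SAP section 8.1 calls a deviation clinically important if it leads to exclusion from an analysis set or could affect key objectives. The PK analysis set leaves out subjects with major deviations or events that would affect PK. Deviation 700 as worded would flag voriconazole and would not flag fluvoxamine. Dose proportionality (protocol 8.5.4.2, SAP 16.1.4) is analysed on that set. At a dose level with a single cohort of 3, one subject carries 1/3 of the weight in the mean log AUC.

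**Working it through.** No sample-size or error-rate figure is involved, so the check is one of set membership.

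**Inputs.** The rule is the bracketed criterion in Appendix II. The grades are the cells of Table 14, which name 58 different drugs. Only three of these appear under more than one enzyme; the other 55 appear under one enzyme only.

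| Drug | CYP2C9 | CYP2C19 | CYP3 | Enzymes at moderate or strong |
|---|---|---|---|---|
| fluconazole | moderate | strong | moderate | 3 |
| fluvoxamine | weak | strong | moderate | 2 |
| voriconazole | weak | weak | strong | 1 |

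**Stated rule: at least 2 enzymes at moderate or strong.** Fluconazole (3) and fluvoxamine (2) qualify. Voriconazole (1) does not. A drug listed under a single enzyme cannot score above 1, so no other entry qualifies.

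**Other readings of the class:**

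| Reading | Drugs selected |
|---|---|
| Moderate or strong on at least 2 (the stated rule) | fluconazole, fluvoxamine |
| Moderate or strong on all 3 | fluconazole |
| Strong on at least 2 | none |
| Any strength on at least 2 | fluconazole, fluvoxamine, voriconazole |
| Any strength on all 3 | fluconazole, fluvoxamine, voriconazole |
| Any strength on all 3, at least 1 strong | fluconazole, fluvoxamine, voriconazole |
| Strong on CYP3, plus any strength on another | voriconazole |

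The pair named in section 6.5.4, fluconazole and voriconazole, is not among the results.

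**Could a damaged table explain it?** For fluconazole and fluvoxamine, no: footnotes a and b give in words the grades that make them qualify. Voriconazole's grades rest on the cells alone, but it appears separately in the CYP2C9 weak, CYP2C19 weak and CYP3 strong cells.

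**Does the SAP add independent evidence?** Little. It is version 1.0, dated 20 Apr 2018, and refers to protocol version 2.0. The protocol's amendment history places the update of Appendix II in version 3.0 (27 August 2019). Deviation 700 may have agreed with the appendix of its time. The conflict between section 6.5.4 and Appendix II stands without it.

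**The case against.** The best reply has four parts.

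*The list is not closed in practice.* Section 6.5.4 points to Appendix II, and a careful reader would find fluvoxamine through the rule and footnote b. That is fair, but the reader would then hold two answers and no statement of which governs.

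*Voriconazole can be defended.* Section 6.5.4 speaks of inhibitors of all three enzymes, and Table 14 lists voriconazole under all three, strongly on CYP3. On that reading its inclusion is right, but fluvoxamine is listed under all three as well, so its omission remains. Joining two rows of the table above (strong on CYP3 plus another enzyme, or at least moderate on all three) would give the named pair, but the protocol states no such rule.

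*The table is illustrative.* A reader might infer that a site would replace all 58 drugs because of the table's title. The documents do not support that: the introduction limits the class, the weak inhibitors sit in their own column, and the note says that the entries are examples. What stands is that nothing marks which entries meet the combined rule. The note does not settle the main conflict, because both disputed drugs are graded in the table.

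*PK-set exclusion does not hang on deviation 700.* The set's definition is wider, concomitant medications are coded and listed, and the data review meeting makes the final assessment. This stands. A subject on fluvoxamine could still be caught there, so an effect on the PK set is possible rather than certain.

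The contrast between section 6.5.2.1 and the SAP's category of disallowed medications is slight: a precaution is not a prohibition, and the SAP term is a label. A cross-reference is enough.

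**Conclusion.** The inconsistency is real and lies within the current protocol, but it is minor. It bears on the instruction to sites and on which subjects are flagged for possible exclusion from the PK set, and through that on the dose-proportionality analysis. The conclusion rests on Table 14's grades as printed. Any effect on results depends on a subject actually taking one of the disputed drugs, and the documents give no frequency for that.

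Three stronger conclusions are tempting and are not supported.

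- *The DLT model is corrupted.* The Dose Escalation set turns on Cycle 1 dosing and on DLTs, not on concomitant drugs. A subject on fluconazole enters the model exactly as one on fluvoxamine does, so correcting the list leaves the composition of that set unchanged. The DLT definition also lets the SMC set aside events due to concomitant medication.
- *The concentration-QTcF model is biased.* SAP section 15.7 regresses QTcF change on measured concentration, which already carries any rise in exposure. No bias is shown.
- *The exposure error can be sized.* One might apply the weak-to-moderate bands in the Table 14 note (1.25-fold to under 5-fold) and read a 35 mg subject as having up to the exposure of 35 × 5 = 175 mg. Those bands describe sensitive index substrates, and section 3.3.1 does not say that its moderate uses them. No two-enzyme effect is given for M8891, and section 3.3.1 reports exposure that seems less than proportional at 60 mg.

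**What to change.** 1. Reconcile section 6.5.4, the Appendix II rule with Table 14, and SAP deviation 700, so that one rule and one list apply throughout. The rule can be changed to yield the intended drugs, or the list changed to follow the rule. Which drugs belong on it is for the sponsor's clinical pharmacologist.
2. Mark in Table 14 which entries meet the combined-inhibitor rule and which are single-enzyme examples.
3. In section 6.5.2.1, add a cross-reference to section 6.5.4.
4. Carry the agreed list into deviation 700 when the SAP is next amended, so that the data review meeting applies the same definition as the sites.

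The cost is wording in two protocol sections, one appendix and one SAP row. Concomitant medications are already recorded in the eCRF (section 6.5) and coded (SAP section 12), so no new data are needed.
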